Recent advances in continuous glucose monitoring (CGM) technology including greater accuracy, longer wear time, and no need for calibration, have led to an increase in use.¹² Randomized controlled trials of modern devices demonstrate improvement in A1c, time target range, hypoglycemia and patient reported outcomes in persons with type 2 diabetes (T2D).^{13,14,15} Moreover, real-world evidence demonstrates a reduction in A1c, diabetes distress, and hypoglycemia, and high ease of use.¹⁶ Other real world evidence found an association between near-continuous CGM and reduced hospitalizations and acute diabetes complications.^{17,18} Among older adults, treatment satisfaction and use was high, and associated with improvement in glucose control.^{19,20} However CGM is underutilized for most patients with T2D due to a variety of factors, including costs and coverage issues, time constraints imposed by implementation and use, and complexity of obtaining and interpreting data.^{12,21} In addition, there limited studies addressing optimal strategies for implementation in busy clinics. In this study we evaluate a remote CGM program utilizing Dexcom G6 CGM for recently hospitalized patients with T2D.

Aim 1: Determine the efficacy of CGM following hospital discharge among patients with T2D. We will record change in glucose metrics from discharge to 12 weeks follow-up, including % time in range 70-180 mg/dl (TIR), % time below 70 mg/dl, 54 mg/dl, and above 180 mg/dl (TAR), severe (level 3) hypoglycemic events, mean glucose, coefficient of variation, and A1c. **We will assess the primary objective by testing the relationship between CGM use (including prior inpatient use) and either change in glucose metrics or individualized % of TIR.**

Aim 2: Evaluate the utility of CGM use and impact of remote monitoring dashboard among recently hospitalized patients with T2D. A dashboard will identify patients not meeting personalized % TIR, triggering customized reports and decision support to be communicated to the patient and the usual diabetes provider. We will assess the proportion of patients with successfully transmitted data as well as change in insulin dose. A survey to the usual diabetes provider will assess usability of reports and decision support.

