| Diabetes history | x | | | | | | | |
| Hospitalization history | x | | | | | | | |
| MSPSS scale | x | | | | | | | |
| eHEALS score | x | | | | | | | |
| SNS3 | x | | | | | | | |
| DTSQ (original plus change at screen and week 12) | | | | | x | | | |
| DDS | x | | | | x | | | |
| BenCGM, BurCGM | | | | | x | | | |
| Additional patient questions | | x | x | x | x | | | x |
| Patient barriers | | | | | | | | x |
| Ascertain health care utilization | x | x | x | x | x | x | x | x |
| Record CGM data | | x | x | x | x | | | x |
| Adverse events | | x | x | x | x | x | x | x |
| Insulin/DM medication use | x | x | x | x | x | x | x | x |
| A1c | x | | | | x | | | x |
| Usual Provider Survey | | | | | x | | | |

CMN=certificate of medical necessity, MSPSS=Multidimensional Scale of Perceived Social Support, eHEALS=eHealth Literacy Scale Diabetes, DTSQ=Diabetes Treatment Satisfaction Questionnaire, BenCGM=Benefit of CGM score, BurCGM=Burdens of CGM score,

DDS=Diabetes Distress Scale, SNS3=Subjective Numeracy Scale-3. In-Person clinic visits will be conducted at either Outpatient Care East or McCampbell Hall. Telephone visits may be converted to in-person visits as needed.

Initial Assessment: Trained interviewers will perform initial data collection.

- Contact information, including email address, best times to reach the patient, contact information for 2 additional individuals, and primary care provider (PCP).
- Demographics, medical, social history
- Multidimensional Scale of Perceived Social Support (MSPSS): Social support is an environmental factor that is associated with readmissions⁴⁹, determines behavior in SCT and influences self-efficacy⁵⁰ and will be measured using the MPSS.⁵¹
- Electronic health literacy: Baseline perceived eHealth literacy will be measured by the eHealth Literacy Scale (eHEALS), in which a score of 28 was used as the cut-off for high or low ehealth literacy.⁵² The scale is comprised of 8 items on a 5-point Likert scale from 1 (strongly disagree) to 5 (strongly agree).
- Subjective Numeracy Scale-3 (SNS-3): The SNS-3 is a validated 3-item version of the longer SNS that was found to be reliable and valid to be used as a measure of subjective numeracy.⁵³

- Comorbidity is key determinant of readmission; it is measured with the Charlson comorbidity index.⁵⁴

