 - **Inclusion/exclusion criteria:** The patient's usual care provider (primary care or endocrinologist) will be identified from the electronic medical record and via patient self-report. Providers will be invited to anonymously respond to the survey via an electronic communication (Inbox message, email, or letter with a URL link—in case of external provider).
- **Week 1, 2, 4, 8, and 12:**
 - **Patients NOT meeting targets:** At 1-2, 4, 8, and 12 weeks, the study team will:
 - Provide advice to the patient on basal insulin titration.
 - Counsel patient on therapeutic lifestyle changes
 - Provide a letter with a summary of the CGM interpretation and counseling provided to the patient as well as any additional advice to the usual diabetes care provider using a standardized template. The letter will include a copy of the Ambulatory Glucose Profile and the Glucose Overlay from the previous 14 days.
 - **Patients meeting targets:** a summary letter with Ambulatory Glucose Profile will be sent to usual care providers at weeks 1-2, 4, 8, and 12.
- **Week 8:** In preparation for transitioning patient to the extension phase of the study, the usual care provider will be sent instructions for prescribing the CGM device, including a pre-filled certificate of medical necessity, if applicable.

Follow-up Encounters: Patients will be contacted 1-2 weeks after discharge to confirm CGM use and address any concerns. If needed, this visit can be converted to in-person if additional supplies and/or training is needed. Thereafter, in-person visits are only required for the completion of A1c and patient reported outcomes surveys and other visits can be completed via telephone call. Dexcom supplies will be shipped directly to patients monthly or can be picked up by the patient. CGM data will be reviewed on Clarity and sent to the usual diabetes care provider after every visit as noted above. Diabetes medications and healthcare utilization will also be reviewed at each visit. At the 12 week visit, patients will complete patient-reported outcomes surveys and A1c.

Study Completion

Participants will receive an order to complete the A1c at 12 weeks via point-of care assay. They will be asked to complete additional surveys (Table 5). The study team will complete the 12 week visit and send a final communication to the healthcare provider with a summary of the visit, notice of study completion with study extension phase, the patient's Clarity sharecode, and CGM report.

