The database used for this study is REDCap, which is a secure web-based application for building and managing data. It is designed specifically for clinical research and administered by the OSU Center for Clinical and Translational Research. Permission for data access or entry will be granted or revoked at a level that is appropriate for each individual involved in the study. Following verification, data will be locked. Data and data labels can be downloaded selectively (for interim progress reports) or in entirety (end of study) directly from REDCap in SAS or Excel format.

Baseline Data:

- Demographics: gender, race/ethnicity, age, marital status, education, employment, insurance, marital status, contact information
- History: diabetes duration, tobacco use, microvascular/macrovascular complications, heart failure, conditions requiring anticoagulation (thromboembolism, atrial fibrillation), hypertension, hyperlipidemia, liver disease, hypoglycemia awareness, reason for hospital admission
- Medications: pre-admission, discharge, and follow-up insulin use and total daily dose, insulin type, other glucose-lowering medications, steroid use, anticoagulants, antiplatelets
- Exam: weight, height, BMI
- Surveys: MPSSS, eHEALS, SNS-3
- Labwork: eGFR, A1c, glucose level on admission and discharge
- Patient reported outcomes: DTSQs, DDS
- Additional patient questions about CGM use
- CGM target (Table 4)

Visit 1, 2, 3:

- Glucose data: detailed below
- Communication: to usual care provider (summary only, summary with advice)
- Diabetes medications, bolus insulin use, basal insulin dose, missed doses
- Adverse events (sensor irritation, infection, bleeding)
- Additional patient questions about CGM use
- Healthcare Utilization: PCP visit, education visit, endocrinology visit, hospital readmission, emergency visit
- CGM target (Table 4)

Visit 4:

- Glucose data: detailed below
- Communication: to usual care provider (summary only, summary with advice)
- Diabetes medications: non-insulin medication use by class, bolus insulin use, basal insulin dose, missed doses
- Adverse events (sensor irritation, infection, bleeding)
- Healthcare Utilization: PCP visit, education visit, endocrinology visit, hospital readmission, emergency visit
- Patient reported outcomes: DTSQs, DTSQc, DDS, BenCGM, BurCGM
- Additional patient questions about CGM use
- A1c
- CGM target (Table 4)

Visit 5, 6

- Glucose data: detailed below

Visit 7

- Glucose data: detailed below

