- Diabetes medications: non-insulin medication use by class, bolus insulin use, basal insulin dose, missed doses
- Adverse events (sensor irritation, infection, bleeding)
- Healthcare Utilization: PCP visit, education visit, endocrinology visit, hospital readmission, emergency visit
- A1c
- Additional patient questions about CGM use, barriers to use

Glucose data: A minimum of 14 consecutive days with 70-80% of data overall is recommended for analysis.⁶²

- Coefficient of variation (CV) is calculated as the standard deviation/mean glucose and is the preferred measure of glucose variability.
- % Time in target range (TIR) 70-180 mg/dl
- Hyperglycemia
 - Time spent >180 mg/dl (TAR)
 - Time spent >300 mg/dl
- Hypoglycemia
 - Time spent <54 mg/dl
 - Time spent <70 mg/dl (TBR)
- Additional Measures
 - Mean sensor glucose
 - % time of CGM data
 - Sensor Failures

Usual care providers: usual care providers will complete a 12 item questionnaire which will include

- provider type
- years in practice

- practice setting
- specialty
- % of patients with diabetes (5-level category)
- familiarity with CGM (5-point Likert)
- frequency of CGM interpretation (4 level category)
- 5-item Likert scale:
 - SUS-2 (ease of use, cumbersome to use)
 - CGM report helpful in assessing glucose control
 - ambulatory glucose profile helpful for making adjustment in therapy
 - report recommendations helpful for making adjustments to therapy
- Whether Clarity website was accessed

Endpoints:

Aim 1:

Primary

- Change % TIR 70-180 mg/dl from baseline (week 2) to 12 weeks

Secondary

- Change in % of patients meeting individualized TIR (Table 3)
- Change % TAR, TBR, % time <54 mg/dl, mean glucose, CV from baseline to 12 weeks
- Change in A1c from baseline to 12 weeks

Aim 2:

Primary

- % CGM wear time at 12 weeks

Secondary

- % of patients with % wear time >70% at 12 weeks.
- Reason for CGM wear <70% (loss to follow-up, issue with mobile phone, sensor/transmitter loss or damage, adverse sensor event, patient preference [state reason], other)
- % with transmitted data at 12 weeks
- % with dashboard driven summary, dashboard driven advice sent to usual care provider by 12 weeks
- Change in basal insulin dose from discharge to 12 weeks

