Usual Care Provider: usual care providers will complete a 12 item questionnaire which will include the 2 item provider type, years in practice, practice setting, specialty, % of patients with diabetes, familiarity with CGM, frequency of CGM interpretation, SUS-2 (ease of use, cumbersome to use), CGM report helpful in assessing glucose control, ambulatory glucose profile helpful for making adjustment in therapy, report recommendations helpful for making adjustments to therapy, whether Clarity website was accessed.

Potential Risks

There are no physical risks that would not otherwise be anticipated, as the blood draw for A1c is considered standard of care. No specific prescriptive regimen for medications is planned and therefore this also represents standard of care. Participants undergoing interstitial glucose monitoring, while considered a standard of care practice, may experience discomfort during sensor insertion, or difficulty with sensor adhesive such as irritation, pruritus, rash, or infection. In a study of the Dexcom G4, no device related serious adverse events occurred during the study (N=158).¹⁴ While the frequency of mild skin irritations with the Dexcom G6 have not been reported in a recent study,⁶³ mild reactions such as erythema, bruising, bleeding, infection have been reported with other devices, and may lead to device discontinuation.⁶⁴ Sensor accuracy may be affected by rapid changes in glucose, acute illness, theoretically resulting in over- or undertreatment of high or low glucose levels. However, studies have demonstrated that overall glucose control, including A1c, is improved and hypoglycemia risk is reduced. While the sensor is FDA approved for use up to 10 days, actual sensor life may vary. Psychological harm may be a possibility if participants neglect other aspects of self-care in favor of diabetes. However, this seems unlikely and will be averted with frequent contact and anticipated increased outpatient follow-up. No financial or legal consequences are anticipated. Breach of confidentiality is a possibility but with standard procedures for immediate entry of paper data into the secure online database, use of a study identification code on all data gathering instruments, and the use of electronic health records, this should be limited.

Usual Care Providers: the survey will pose limited risk, breach of confidentiality is very low as an anonymous electronic link will be provided.

Adequacy of Protection Against Risks

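### Aim 1 promises severe (level 3) hypoglycemic events, but they are undefined, are not an endpoint under any aim, and are not a named item at any visit, so they cannot be counted systematically

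*Combined protocol and SAP*

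**What the plan says.** Under Specific Aims, Aim 1 lists the glucose outcomes to be recorded between discharge and 12 weeks. After the time-in-range percentages it names "severe (level 3) hypoglycemic events, mean glucose, coefficient of variation, and A1c". Level 3 hypoglycemia is mentioned nowhere else in the document.

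In the Endpoints section, the Aim 1 primary endpoint is "Change % TIR 70-180 mg/dl from baseline (week 2) to 12 weeks". The secondary endpoints are the share of patients meeting individualized time in range, "Change % TAR, TBR, % time <54 mg/dl, mean glucose, CV from baseline to 12 weeks", and change in A1c. No hypoglycemic event appears there, or under Aim 2, Aim 3 or the exploratory aims.

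The data to be collected are listed twice, under Data Collection and Management and under Sources of Materials in the Human Subjects section. For visits 1 to 4 and visit 7, both lists give "Adverse events (sensor irritation, infection, bleeding" and nothing further in that item. For visits 5 and 6, both give glucose data only. The hypoglycemia items under Glucose data are "Time spent <54 mg/dl" and the corresponding time below 70 mg/dl.

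Table 5 has an adverse-event row ticked at visits 1 to 7 and a health care utilization row ticked at every visit. Neither row's content is described in the table.

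**The concern.** An outcome named in an aim should have a definition, a place where it is recorded and a line in the endpoints. This one has none of the three. If staff build the forms from the data lists, nobody is prompted to ask about a severe episode.

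All participants are on basal insulin, and those missing their targets are given advice on titrating it at the scheduled contacts, so the outcome is a natural companion to any reported gain in time in range. The Work Plan also foresees a poster and a manuscript carrying safety data. A report of no severe events would leave the reader unable to tell whether none occurred or none was asked about. What is not asked at the time is hard to recover at analysis.

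**Working it through.** No arithmetic applies: the plan gives no expected rate or target precision for these events. The check sets the sections side by side.

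**Step 1. Aim 1 against the Aim 1 endpoints.** The Aim 1 sentence holds eight outcomes.

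- Time in range: primary endpoint.
- Time below 70 mg/dl: secondary endpoint (TBR).
- Time below 54 mg/dl: secondary endpoint.
- Time above 180 mg/dl: secondary endpoint (TAR).
- Mean glucose: secondary endpoint.
- Coefficient of variation: secondary endpoint.
- A1c: secondary endpoint.
- Severe (level 3) hypoglycemic events: absent.

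Seven of eight carry over, and the one dropped is the only event outcome.

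**Step 2. Could the glucose data supply it?** The Glucose data list contains percentages of time, mean, variability, percentage of data captured and sensor failures. It contains no event of any kind, and the plan gives no rule for deriving a level 3 event from sensor readings. Being listed separately in Aim 1 does not by itself show that a sensor download cannot supply the outcome, because mean glucose and coefficient of variation are also listed separately and do come from the sensor. The gap is that no definition exists and no item on the list is an event.

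**Step 3. Could another route supply it?**

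- *Adverse-event item.* The three examples are sensor or skin problems. Table 5 adds no further content.
- *Health care utilization.* Emergency visits and readmissions are recorded, but the reason is not requested.
- *Adverse event reporting under Protections against risk.* Severe adverse events go to the principal investigator and the IRB. There is no prompt for hypoglycemia.
- *DTSQ.* One item asks how often low glucose is perceived; it does not count severe episodes.
- *Baseline history.* Hypoglycemia awareness is recorded, but prior severe episodes are not.

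An episode that led to health care contact might surface through the second or third route. An episode handled at home has no named place in any of them.

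**Step 4. Do the lists and Table 5 agree?** Not at visits 5 and 6. Table 5 ticks adverse events, utilization and medication use there and leaves the CGM data row blank; both lists give glucose data only. So the lists cannot be read as the full content of Table 5, and Table 5 does not supply the missing content either.

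**Step 5. Is a change from baseline possible?** Aim 1 speaks of change from discharge. With no look-back for severe episodes at baseline, there is nothing to subtract. Only a count over follow-up can be reported.

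**The case against.** The strongest reply is that the plan is not silent on harm. Table 5 has an unrestricted adverse-event row at seven visits, severe adverse events are reportable, emergency visits and readmissions are recorded, and medical records are monitored. The three examples in parentheses may be only illustrations, and the mismatch at visits 5 and 6 shows that the lists are not exhaustive. This stands as far as it goes. A reader might infer that the trial cannot report these events at all, or that every event without a clinic visit is lost. The documents do not support that. What they show is the lack of any named, systematic item.

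A reader might also take level 3 hypoglycemia to be the trial's main safety outcome. No section says so: it sits among the glucose outcomes of an efficacy aim, and safety outcomes are not ranked.

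Finally, a reader might see a contradiction between the instruction "Provide advice to the patient on basal insulin titration" and the Potential Risks statement "No specific prescriptive regimen for medications is planned and therefore this also represents standard of care". Advice to a patient can coexist with the absence of a prescribed regimen, so this is not a clear contradiction. It is also a separate matter on which the present point does not depend.

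**Conclusion.** The point holds as an internal inconsistency. One of the eight outcomes promised in Aim 1 has no definition, no endpoint and no named data item, so it cannot be counted systematically and a zero count would not be interpretable. Some events may still be picked up through the general routes.

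No figure can be put on the number missed, because the plan gives no event rate. A confidence limit for zero events in the planned sample would describe a trial that asked the question, so it does not measure this gap.

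The conclusion assumes that the case report forms follow the data lists. If the forms, which are not part of the document, already contain the question, what remains is to define the event, add the endpoint and bring the protocol into line. The change should be made, but the primary endpoint and the sample size are untouched.

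**What to change.** 1. State in the protocol what counts as a severe (level 3) hypoglycemic event.
2. Add it to the adverse-event items at the follow-up contacts where Table 5 already ticks adverse events (visits 1 to 7). Record whether an event occurred, how many, the date, and any resulting emergency visit or admission.
3. Align the visit 5 and 6 entries in both data lists with Table 5.
4. Add it to the Aim 1 secondary endpoints as the proportion of patients with at least one event and the number of events per patient-time, from discharge to week 12. Do not report it as a change, since no baseline look-back is collected. Because 20% drop-out is expected (0.20 × 120 = 24 patients), state the denominator for the proportion and let patients who leave early contribute their observed time to the rate.
5. Treat events to week 24 as descriptive only, since Aim 1 ends at 12 weeks.

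The cost is a few REDCap fields at contacts that already take place, a definition, and one line in the Endpoints. No extra visits or staff are needed.

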- Usual Care Provider usability: SUS-2 (ease of use, cumbersome to use), CGM report helpful in assessing glucose control, ambulatory glucose profile helpful for making adjustment in therapy, report recommendations helpful for making adjustments to therapy, whether Clarity website was accessed.
- % of usual care providers reporting review of data

Aim 3:

Primary:

- Change in DTSQ scores from baseline to 12 weeks

Secondary:

- Change in DDS from baseline to 12 weeks
- Patient reported outcomes (DTSQ, DDS, BenCGM, BurCGM).

Endpoints for Exploratory Aim 1:

- healthcare utilization (clinic visits, education visit, hospital readmission, emergency visit)

Endpoints for Exploratory Aim 2 (Extension Phase): *By 18 months (the end of the last 90 day visit), we anticipate that a subset of patients (75%) will have at least 12 additional weeks of data following the primary endpoint at 12 weeks. We will assess the following metrics among users and compare to nonusers:*

- Change in % CGM wear from 12 weeks to 24 weeks
- Change in glucose metrics from 12 weeks to 24 weeks.
- Change in insulin dose from 12 weeks to 24 weeks.
- Patient reported barriers to continued CGM use (5-point Likert from not important at all to very important, unless otherwise noted):
 - Cost/coverage concerns (if important or very important, then answer the following)

- Insurance did not cover CGM (yes/no)
- Insurance partially covered CGM but co-pay was too high (yes/no)
- Usual care provider would not prescribe CGM (yes/no)
- Too much hassle to order/obtain CGM
- Too many alarms
- Having device attached to the body/lack of privacy
- Do not understand what to do with the information
- Unreliable/does not work
- Discomfort/pain
- Too time-consuming
- Interferes with sleep
- Healthcare utilization (PCP visit, education visit, endocrinology visit, hospital readmission, emergency visit)

Sample Size

We anticipate enrollment of 120 patients over a 1 year period with 20% drop-out. The following data support this sample size.

Aim 1:

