- %TIR: Beck et al reported time in target 70-180 mg/dl per day increased from median 802 (IQR 604-974) to 937 (664-1083) minutes from baseline to 12 weeks. This is commensurate with a % TIR of 55.7% and 65.1% respectively.¹⁴ In a study of 25 older patients with either type 1 or type 2 diabetes (N=25) who wore the Dexcom G4 for 4 weeks, the % TIR increased from 66.3 (SEM 2.6) to 76.9% (SEM 3.0), the TBR decreased from 9.6 (SEM 2.1) to 5.2 (SEM 1.1)%, the TAR decreased from 23.9 (SEM 3.0) to 17.9 (3.1), and the CV decreased from 37.3 (SEM 2.3) to 32.9 (SEM 1.3).¹⁹ In the MOBILE study, the % time in target range was 59%.¹⁵ Thus, we estimate a sample size of 80 will yield 99% power to detect a 15% difference from a hypothesized mean of 60% TIR, a standard deviation of 15 and significance level of 0.05.
- % Individualized TIR: In the LANDMARK study, a total of 47% of subjects met the target of 70% TIR. In this study we will use individualized target time in range (Table 3) and thus anticipate a greater proportion of participants (60%) meeting the individualized % TIR.¹⁶
- A1c: In the real-world LANDMARK study, A1c fell from 8.5 +/- 2.2% to 7.1 +/- 1.1% in 66 patients with T2D at 12 weeks following Dexcom G6 CGM initiation.¹⁶ Beck et al reported the A1c decreased from 8.5% to 7.5 (IQR 7.4-7.7), a reduction of 1.0 (IQR -1.2 to -0.8).¹⁴ In the MOBILE study, the A1c decreased 1.3 (1.0)% in the CGM group and -0.7 (0.9%) in the control group.¹⁵ Thus, a sample size of 80 will yield 98% power to detect a 0.4% difference from a hypothesized mean 0.7% reduction in A1c, assuming a standard deviation of 0.9%, and significance level of 0.05.

Aim 2:

- % Wear time: In a randomized study using the Dexcom G4 system (a 7 day sensor), the % of possible CGM readings (excluding 2 hours after each new sensor insertion) was mean 92 (SD 15), median 97 (IQR 92-99) at week 12 of use, or approximately 92% wear time.¹⁴ In the MOBILE study, the median wear time was 6.3 (IQR 5.4, 6.7).¹⁵ We would anticipate a lower wear time with the current study due to differences in the study population. Thus, a sample size of 80 will yield 99% power to detect a 1 day difference from a more modest hypothesized mean 6.3 days of wear time, a standard deviation of 0.96, and significance level of 0.05.

Aim 3:

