- DTSQ: In the LANDMARK study, 94% of participants with T2D were satisfied or very satisfied (Question 1 of the DTSQ). In a randomized study of 101 patients with T2D using the Freestyle Libre Flash glucose monitor (an intermittently scanned glucose monitoring device), mean (SD) DTSQc score per subject for each question was 2.47 (0.77) with CGM vs. 2.18 (0.83) in the control group ($P = 0.053$). Thus, we would anticipate a change in DTSQc that is proportional.¹³
- DDS: In the LANDMARK study, the DDS decreased from 2.67 (SD 0.65) to 1.85 (0.65) from baseline to 12 weeks. We would anticipate a similar change in DDS score.
- BenCGM, BurCGM: In a large study of patients with type 1 diabetes, there was a significant difference in BenCGM (4.48 vs. 4.19, $p<0.001$) and BurCGM (1.69 vs. 2.35, $p<0.001$) among CGM users vs. non-

users, respectively. Thus, we anticipate that both scores will be associated with CGM wear time in the present study.

Analysis

Descriptive statistics will summarize the sample characteristics and distribution of each variable. Data will be screened for normality, outliers, and homogeneity. Continuous variables with normal distribution will be reported as mean (standard deviation) while non-normal distribution will be reported as median (interquartile range). Binary variables will be reported as number (percentage). Change over time in continuous variables will be reported as paired t-test or nonparametric test as appropriate. Difference of proportions between groups for binary variables is tested by Fisher's test (two groups) or chi-square test (three or more groups). Statistical significance will be determined at p-value of <0.05.

For Aim 1, linear regression can be used for checking the relationship between %CGM wear time and change in glucose metrics. Appropriate transformation may be needed if the residual plots show obvious violation of linear regression assumptions. Logistic regression can be used for checking the association between % CGM wear time and % meeting individualized TIR or change in % of patients who meet their individualized TIR. For choosing the predictors of change in TIR from baseline to 12 weeks, we can first include a subset of the exploratory variables depending on the descriptive statistics and clinical context. If necessary, further variable selection (stepwise selection) can be conducted to make the analysis reliable. In addition, we will assess baseline predictors of glucose metrics.

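### Aim 1 has two different primary analyses: Specific Aims tests an association with either of two kinds of outcome, Endpoints ranks only change in % TIR primary, and Analysis labels no test primary

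*Combined protocol and SAP*

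**What the plan says.** **Specific Aims, Aim 1.** Change from discharge to 12 weeks will be recorded for TIR, time below 70 and below 54 mg/dl, time above 180 mg/dl, and "severe (level 3) hypoglycemic events, mean glucose, coefficient of variation, and A1c". A sentence in bold then assesses the "primary objective by testing the relationship between CGM use (including prior inpatient use) and either change in glucose metrics or individualized % of TIR".

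**Endpoints, Aim 1.** One item is primary: "Change % TIR 70-180 mg/dl from baseline (week 2) to 12 weeks". The secondary items are "Change in % of patients meeting individualized TIR (Table 3", "Change % TAR, TBR, % time <54 mg/dl, mean glucose, CV from baseline to 12 weeks", and change in A1c. Severe hypoglycemic events are not in this list.

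**Analysis.** "Change over time in continuous variables will be reported as paired t-test or nonparametric test as appropriate". For Aim 1 the section adds that linear regression can relate wear time to change in glucose metrics, and that logistic regression can relate wear time to meeting individualized TIR. The significance level is 0.05. No test is labelled primary and no multiplicity rule is given.

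**Sample Size.** "We anticipate enrollment of 120 patients over a 1 year period with 20% drop-out". For TIR, 80 patients are said to give "99% power to detect a 15% difference from a hypothesized mean of 60% TIR, a standard deviation of 15".

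**The concern.** An association between CGM use and an outcome is a different question from the mean change in that outcome over time. One can be positive while the other is null. Specific Aims makes the first question primary and leaves the outcome open. Endpoints makes a change primary and fixes the outcome. An analyst who follows Specific Aims could report individualized TIR, or another metric that Endpoints ranks secondary, as the result that settles the primary objective. Because Analysis labels no test primary, the choice could be made after the data are seen, and a reader could not tell.

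**Working it through.** **1. The sections side by side (Aim 1).**

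| | Specific Aims | Endpoints (primary) | Analysis |
|---|---|---|---|
| Outcome | glucose metrics, or individualized TIR | % TIR only | glucose metrics; individualized TIR |
| Contrast | association with CGM use | change over time | both, neither labelled primary |
| Exposure | CGM use, including prior inpatient use | none | % wear time |
| Start point | discharge | week 2 | not stated |

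The sections overlap at one point: change in TIR could be the outcome of the association. They agree on nothing else in the table.

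**2. The plan's own power figure.** Inputs from Sample Size: n = 80, difference 15, SD 15, alpha 0.05 (two-sided assumed). Power = Φ(difference/SD × √n − 1.96).

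- As stated: 15/15 × √80 − 1.96 = 8.94 − 1.96 = 6.98, so power is above 0.9999.
- With 15% read as relative, 0.15 × 60 = 9 points: 9/15 × 8.94 − 1.96 = 3.41, so power is 0.9997.
- With an assumed SD of change of 24 and a 15-point difference: 15/24 × 8.94 − 1.96 = 3.63, so power is still above 0.999.

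The stated 99% is met in each case. This calculation is for a mean, not for an association.

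**3. The association, which has no power statement.** By Fisher's z, the correlation detectable with 80% power is tanh[(1.960 + 0.842)/√(n − 3)].

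- n = 80: tanh(2.802/8.775) = tanh(0.319) = 0.309.
- n = 96 (120 less 20%): tanh(2.802/9.644) = tanh(0.291) = 0.283.
- At n = 80, power is 0.43 for r = 0.2 and 0.78 for r = 0.3.

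**4. Error rate if either of two outcomes could satisfy the objective.** Each is tested at two-sided 0.05. If independent, 1 − 0.95² = 0.0975. For correlated normal test statistics the rate is 1 − P(both |Z| ≤ 1.96):

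| Assumed correlation | 0 | 0.3 | 0.7 | 0.9 |
|---|---|---|---|---|
| Error rate | 0.0975 | 0.095 | 0.084 | 0.070 |

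The documents give no correlations, so the result is a range of about 7% to 10%.

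**The case against.** The strongest reply is that Endpoints is the section that ranks outcomes, and it names one Aim 1 primary with its metric and window. Analysis assigns a paired or nonparametric test to changes in continuous variables, so the primary test can be inferred. On this view the either/or wording only lists outcome types that match the linear and logistic models in Analysis. Much of this stands: it would be wrong to say that the plan names no primary outcome. But nothing says that Endpoints overrides the sentence describing how the primary objective is assessed, and the inferred test still leaves a choice between parametric and nonparametric forms.

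Two smaller replies also have some force. Prior inpatient use could fall under the baseline predictors that Analysis plans to examine, though Analysis does not name it. Discharge and week 2 could be the same baseline if it is the first 14 days of sensor wear, since the plan recommends at least 14 consecutive days of data. The text does not say so.

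A reader might infer a much larger error rate. The eight listed metrics plus individualized TIR make nine outcomes, and nine independent tests give 1 − 0.95⁹ = 0.370 (0.124 at an assumed correlation of 0.9). The documents do not support that as a headline. Specific Aims states no rule that any one significant result is enough. TIR, TAR and TBR partition sensor time, and individualized TIR is a cut of TIR, so independence cannot hold. Severe hypoglycemia may also be too sparse for a normal test statistic.

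A reader might also infer that the study is too small. The check above does not support that for the TIR comparison.

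**Conclusion.** The contradiction is real and lies in current text. The sections disagree on which outcomes may decide Aim 1, on association versus within-patient change, on the exposure and on the start point. Severe hypoglycemic events have no rank at all.

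The error rate of about 7% to 10% against a nominal 5% assumes that significance on either of two outcomes would count as success. A broader reading of glucose metrics would raise it, but no firm figure can be given. The detectable |r| of about 0.31 at n = 80 describes what the association could show. It is not evidence that the study is underpowered, because the plan gives no expected correlation. This should be fixed before analysis.

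**What to change.** - **Specific Aims:** remove the either/or wording and name change in % TIR from week 2 to week 12 as the only Aim 1 primary outcome. Reconcile discharge with week 2 by stating which sensor days form the baseline.
- **Analysis:** name one primary test of that change in advance, for example the paired t-test with the nonparametric test as a sensitivity analysis.
- **Endpoints and Analysis:** label the associations with wear time and prior inpatient use, and all other outcomes, as secondary. Give severe hypoglycemic events a rank.
- **If the sponsor prefers the association as primary:** name one exposure and one outcome, change Endpoints to match, and state the detectable correlation in Sample Size (about 0.31 at n = 80, 0.28 at n = 96).

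No more patients are needed. The sponsor loses the freedom to choose the primary test later, and under the first option the association in bold becomes secondary. That option has a limit that should be stated: the paired test is an uncontrolled before-after comparison whose baseline is already on CGM, so it cannot by itself attribute a change to CGM.
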